#### 10.4.2.1. Handling of Missing and Partial Dates

Element	Reporting Detail
General	
 
Partial dates will be displayed as captured in subject listing displays.
 

Adverse Events	
 
The eCRF allows for the possibility of partial dates (i.e., only month and year) to be recorded for AE start and end dates; that is, the day of the month may be missing.
 
Completely missing start or end dates will remain missing, with no imputation applied. Consequently, time to onset and duration of such events will be missing.
 
The recorded partial date will be displayed in the listings
 

Concomitant Medications/ Medical History	
 
Partial dates for any concomitant medications recorded in the CRF will not be imputed.
 
The recorded partial date will be displayed in listings.
 

## 10.5. Appendix 5: Values of Potential Clinical Importance

### 10.5.1. Laboratory Values

Haematology				
Laboratory Parameter	Units	Category	Clinical Concern Range	
			Low Flag (< x)	High Flag (>x)
Hematocrit	Ratio of 1	Male	0.03	0.54
		Female	0.04	0.54
Haemoglobin	g/L	Male	110	180
		Female	100	170
Red Blood Cell Count	x10  /L	Male	4.5	5.5
		Female	4	5
Platelet Count	x10  /L		80	400

Clinical Chemistry				
Laboratory Parameter	Units	Category	Clinical Concern Range	
			Low Flag (< x)	High Flag (>x)
Albumin	g/L		30	
Calcium	mmol/L		2	2.75
Creatinine	umol/L			133
Glucose	mmol/L		3	9
Potassium	mmol/L		3	5.5
Sodium	mmol/L		130	150
ALP	IU/L		20	200
ALT/SGPT	U/L	High		≥ 2x ULN
AST/SGOT	U/L	High		≥ 2x ULN

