### 10.7.5. Safety Tables

Safety: Tables					
No.	Population	IDSL / Example Shell	Title	Programming Notes	Deliverable [Priority]
Adverse Events (AEs)					
2.1.	Safety	AE13	Adverse Event Overview - Fed		SAC [1]
2.2.	Safety	AE13	Adverse Event Overview - Fasting		SAC [1]
2.3.	Safety	CP_AE1x	Summary of All Adverse Events - Fed		SAC [1]
2.4.	Safety	CP_AE1x	Summary of All Adverse Events - Fasting		SAC [1]
2.5.	Safety	CP_AE1x	Summary of all Adverse Events by Maximum Intensity - Fed		SAC [1]
2.6.	Safety	CP_AE1x	Summary of all Adverse Events by Maximum Intensity - Fasting		SAC [1]
2.7.	Safety	CP_AE1x	Summary of Drug-Related Adverse Events - Fed		SAC [1]
2.8.	Safety	CP_AE1x	Summary of Drug-Related Adverse Events - Fasting		SAC [1]
2.9.	Safety	CP_AE1x	Summary of Adverse Events Leading to Withdrawals from Study - Fed		SAC [1]
2.10.	Safety	CP_AE1x	Summary of Adverse Events Leading to Withdrawals from Study - Fasting		SAC [1]
2.11.	Safety	CP_AE1x	Summary of Serious Adverse Events - Fed		SAC [1]

Safety: Tables					
No.	Population	IDSL / Example Shell	Title	Programming Notes	Deliverable [Priority]
2.12.	Safety	CP_AE1x	Summary of Serious Adverse Events - Fasting		SAC [1]
2.13.	Safety	CP_AE1x	Summary of Non-Serious Adverse Events - Fed		SAC [1]
2.14.	Safety	CP_AE1x	Summary of Non-Serious Adverse Events - Fasting		SAC [1]
Laboratory: Chemistry					
2.15.	Safety	LB1	Summary of Change from Baseline in Chemistry Laboratory Values - Fed		SAC [1]
2.16.	Safety	LB1	Summary of Change from Baseline in Chemistry Laboratory Values - Fasting		SAC [1]
2.17.	Safety	LB2	Summary of Chemistry Laboratory Values Relative to Potential Clinical Importance Criteria, Day 16 or Early Withdrawal - Fed		SAC [1]
2.18.	Safety	LB2	Summary of Chemistry Laboratory Values Relative to Potential Clinical Importance Criteria, Day 16 or Early Withdrawal - Fasting		SAC [1]
2.19.	Safety	LB4	Summary of Chemistry Laboratory Shifts From Baseline with Respect to the Normal Range - Fed		SAC [1]
2.20.	Safety	LB4	Summary of Chemistry Laboratory Shifts From Baseline with Respect to the Normal Range - Fasting		SAC [1]
Laboratory: Hematology					
2.21.	Safety	LB1	Summary of Change from Baseline in Hematology Laboratory Values - Fed		SAC [1]
2.22.	Safety	LB1	Summary of Change from Baseline in Hematology Laboratory Values - Fasting		SAC [1]
2.23.	Safety	LB2	Summary of Hematology Laboratory Values Relative to Potential Clinical Importance Criteria, Day 16 or Early Withdrawal - Fed		SAC [1]

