Safety: Tables					
No.	Population	IDSL / Example Shell	Title	Programming Notes	Deliverable [Priority]
2.24.	Safety	LB2	Summary of Hematology Laboratory Values Relative to Potential Clinical Importance Criteria, Day 16 or Early Withdrawal - Fasting		SAC [1]
2.25.	Safety	LB4	Summary of Hematology Laboratory Shifts From Baseline with Respect to the Normal Range - Fed		SAC [1]
2.26.	Safety	LB4	Summary of Hematology Laboratory Shifts From Baseline with Respect to the Normal Range - Fasting		SAC [1]
Laboratory: Urinalysis					
2.27.	Safety	LB1	Summary of Urinalysis Dipstick Results - Fed		SAC [1]
2.28.	Safety	LB1	Summary of Urinalysis Dipstick Results - Fasting		SAC [1]
2.29.	Safety	LB4	Summary of Urinalysis Laboratory Shifts From Baseline with Respect to the Normal Range - Fed		SAC [1]
2.30.	Safety	LB4	Summary of Urinalysis Laboratory Shifts From Baseline with Respect to the Normal Range - Fasting		SAC [1]
ECG					
2.31.	Safety	EG1	Summary of ECG Findings - Fed		SAC [1]
2.32.	Safety	EG1	Summary of ECG Findings - Fasting		SAC [1]
2.33.	Safety	EG2	Summary of ECG Values - Fed		SAC [1]
2.34.	Safety	EG2	Summary of ECG Values - Fasting		SAC [1]
2.35.	Safety	EG2	Summary of Mean Change from Baseline in ECG Values - Fed		SAC [1]
2.36.	Safety	EG2	Summary of Mean Change from Baseline in ECG Values - Fasting		SAC [1]
2.37.	Safety	EG1	Summary of the Number and Percentage of Subjects Who Had Abnormal ECG Findings - Fed		SAC [1]
2.38.	Safety	EG1	Summary of the Number and Percentage of Subjects Who Had Abnormal ECG Findings - Fasting		SAC [1]

Safety: Tables					
No.	Population	IDSL / Example Shell	Title	Programming Notes	Deliverable [Priority]
Vital Signs					
2.39.	Safety	VS1	Summary of Vital Signs - Fed		SAC [1]
2.40.	Safety	VS1	Summary of Vital Signs - Fasting		SAC [1]
2.41.	Safety	VS1	Summary of Change from Baseline in Vital Signs - Fed		SAC [1]
2.42.	Safety	VS1	Summary of Change from Baseline in Vital Signs - Fasting		SAC [1]
Pregnancy					
2.43.	Safety	Standard	Summary of Pregnancy - Fed		SAC [1]
2.44.	Safety	Standard	Summary of Pregnancy - Fasting		SAC [1]

- The requirements for each display (i.e. IDSL, ICH, FDAAA etc) specified in the programming notes may be retained, all other red reference notes should be deleted.
- Select appropriate standard based on study design (i.e. parallel vs cross-over), when applicable.
- Suggested IDSL shells are noted in the third column, but other IDSL shells may be used, as appropriate

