28.	Safety	CP_AE9a	Listing of Serious Adverse Events (Overall) - Fasting		SAC [1]

ICH: Listings					
No.	Population	IDSL / Example Shell	Title	Programming Notes	Deliverable [Priority]
29.	Safety	CP_AE9a	Listing of Serious Adverse Events (Fatal) - Fed		SAC [1]
30.	Safety	CP_AE9a	Listing of Serious Adverse Events (Fatal) - Fasting		SAC [1]
31.	Safety	CP_AE9a	Listing of Serious Adverse Events (Non-Fatal) - Fed		SAC [1]
32.	Safety	CP_AE9a	Listing of Serious Adverse Events (Non-Fatal) - Fasting		SAC [1]
33.	Safety	CP_AE9	Listing of All Drug-Related Adverse Events - Fed		SAC [1]
34.	Safety	CP_AE9	Listing of All Drug-Related Adverse Events - Fasting		SAC [1]
35.	Safety	CP_AE9	Listing of Adverse Events Leading to Withdrawal from Study - Fed		SAC [1]
36.	Safety	CP_AE9	Listing of Adverse Events Leading to Withdrawal from Study - Fasting		SAC [1]
37.	Safety	AE7	Listings of Subject Numbers for Individual Adverse Events - Fed		SAC [1]
38.	Safety	AE7	Listings of Subject Numbers for Individual Adverse Events - Fasting		SAC [1]
39.	Safety	AE2	Listing of Hierarchical Relationship of Adverse Event System Organ Class, Preferred Term and Verbatim Text - Fed		SAC [1]
40.	Safety	AE2	Listing of Hierarchical Relationship of Adverse Event System Organ Class, Preferred Term and Verbatim Text - Fasting		SAC [1]
All Laboratory					
41.	Safety	LB6	Listing of Clinical Chemistry Abnormalities of Potential Clinical Importance - Fed		SAC [1]
42.	Safety	LB6	Listing of Clinical Chemistry Abnormalities of Potential Clinical Importance - Fasting		SAC [1]
43.	Safety	LB6	Listing of Hematology Abnormalities of Potential Clinical Importance - Fed		SAC [1]
44.	Safety	LB6	Listing of Hematology Abnormalities of Potential Clinical Importance - Fasting		SAC [1]

ICH: Listings					
No.	Population	IDSL / Example Shell	Title	Programming Notes	Deliverable [Priority]
45.	Safety	LB6	Listing of All Clinical Chemistry Data for Subjects with Potential Clinical Abnormalities - Fed		SAC [1]
46.	Safety	LB6	Listing of All Clinical Chemistry Data for Subjects with Potential Clinical Abnormalities - Fasting		SAC [1]
47.	Safety	LB6	Listing of All Hematology Data for Subjects with Potential Clinical Abnormalities - Fed		SAC [1]
48.	Safety	LB6	Listing of All Hematology Data for Subjects with Potential Clinical Abnormalities - Fasting		SAC [1]
49.	Safety	LB13	Listing of Laboratory Tests and Associated Reference Ranges		SAC [1]

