50.	Safety	LB6	Listing of All Laboratory Values Outside the Normal Reference Range - Fed		SAC [1]
51.	Safety	LB6	Listing of All Laboratory Values Outside the Normal Reference Range - Fasting		SAC [1]
ECG					
52.	Safety	CP_EG4	Listing of ECG Values of Potential Clinical Importance - Fed		SAC [1]
53.	Safety	CP_EG4	Listing of ECG Values of Potential Clinical Importance - Fasting		SAC [1]
54.	Safety	CP_EG4	Listing of All ECG Values for Subjects with a Value of Potential Clinical Importance - Fed		SAC [1]
55.	Safety	CP_EG4	Listing of All ECG Values for Subjects with a Value of Potential Clinical Importance - Fasting		SAC [1]
56.	Safety	CP_EG6	Listing of Abnormal ECG findings - Fed		SAC [1]
57.	Safety	CP_EG6	Listing of Abnormal ECG findings - Fasting		SAC [1]
58.	Safety	CP_EG6	Listing of ECG Findings for Subjects with a Value of Abnormal Finding - Fed		SAC [1]
59.	Safety	CP_EG6	Listing of ECG Findings for Subjects with a Value of Abnormal Finding - Fasting		SAC [1]

ICH: Listings					
No.	Population	IDSL / Example Shell	Title	Programming Notes	Deliverable [Priority]
Vital Signs					
60.	Safety	CP_VS5	Listing of Vital Sign Values of Potential Clinical Importance - Fed		SAC [1]
61.	Safety	CP_VS5	Listing of Vital Sign Values of Potential Clinical Importance - Fasting		SAC [1]
62.	Safety	CP_VS5	Listing of All Vital Sign Values for Subjects with a Value of Potential Clinical Importance - Fed		SAC [1]
63.	Safety	CP_VS5	Listing of All Vital Sign Values for Subjects with a Value of Potential Clinical Importance - Fasting		SAC [1]
Pregnancy					
64.	Safety	Non-Standard	Listing of Pregnancy - Fed		SAC [1]
65.	Safety	Non-Standard	Listing of Pregnancy - Fasting		SAC [1]
Liver Event					
66.	Safety	LIVER5	Listing of Liver Monitoring/Stopping Event Reporting - Fed		SAC [1]
67.	Safety	LIVER5	Listing of Liver Monitoring/Stopping Event Reporting - Fasting		SAC [1]
68.	Safety	LIVER6	Listing of Liver Stopping Event Information for RUCAM Score - Fed		SAC [1]
69.	Safety	LIVER6	Listing of Liver Stopping Event Information for RUCAM Score - Fasting		SAC [1]
70.	Safety	SAFE_L2	Listing of Medical Conditions at Onset of Liver Event - Fed		SAC [1]
71.	Safety	SAFE_L2	Listing of Medical Conditions at Onset of Liver Event - Fasting		SAC [1]
72.	Safety	LIVER7	Listing of Liver Biopsy Details - Fed		SAC [1]
73.	Safety	LIVER7	Listing of Liver Biopsy Details - Fasting		SAC [1]
74.	Safety	LIVER8	Listing of Liver Imaging Details - Fed		SAC [1]

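### The low haematocrit flags in SAP Appendix 5 (0.03 male, 0.04 female, on a 0–1 scale) are roughly tenfold too low against the same table's other rows, and their sex order is reversed

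*SAP*

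**What the plan says.** The haematology table in SAP Section 10.5.1 has a low-flag column (values below x) and a high-flag column (values above x). The haematocrit rows read "Hematocrit Ratio of 1 Male 0.03 0.54" and "Female 0.04 0.54". The stated unit and the 0.54 high flag both fix a 0–1 scale, so 0.03 and 0.04 cannot be read as percentages.

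The next row reads "Haemoglobin g/L Male 110 180"; the female haemoglobin limits are 100 and 170 g/L. The red cell count limits are 4.5 and 5.5 (male) and 4 and 5 (female), in 10^12/L.

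Section 7.3 commits to listings based on these criteria. Section 10.7 uses them in three pairs of haematology displays, each with a Fed and a Fasting version:

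- Tables 2.23–2.24: "Summary of Hematology Laboratory Values Relative to Potential Clinical Importance Criteria, Day 16 or Early Withdrawal - Fed"
- Listings 43–44: "Listing of Hematology Abnormalities of Potential Clinical Importance - Fed"
- Listings 47–48: "Listing of All Hematology Data for Subjects with Potential Clinical Abnormalities - Fed"

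No other section of the SAP restates, corrects or explains the two haematocrit low limits.

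**The concern.** Haematocrit, haemoglobin and red cell count describe the same red cells, so their flags should be of compatible size. The haematocrit low flags are an order of magnitude out of line with the other two rows. They are also the only sex-specific pair in the haematology table in which the male limit is the lower one.

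Clinical laboratory measurements are part of a secondary endpoint (Section 2.2). A flag that cannot fire produces a zero that looks like a safety result: the summary would state that nobody had a low haematocrit of potential clinical importance, whatever the laboratory found.

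**Working it through.** All inputs are from the haematology table in Section 10.5.1.

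| Row | Male low / high | Female low / high |
|---|---|---|
| Haematocrit (Hct, ratio) | 0.03 / 0.54 | 0.04 / 0.54 |
| Haemoglobin (Hb, g/L) | 110 / 180 | 100 / 170 |
| Red cells (RBC, 10^12/L) | 4.5 / 5.5 | 4 / 5 |

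**1. Hb ÷ Hct (g/L)**
- High flags: 180/0.54 = 333.3 (male); 170/0.54 = 314.8 (female).
- Low flags: 110/0.03 = 3666.7 (male); 100/0.04 = 2500 (female).
- Low over high: 11.0 (male); 7.9 (female).

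**2. Hct ÷ RBC (× 1000 gives fL)**
- High flags: 0.54/5.5 = 98.2 (male); 0.54/5 = 108.0 (female).
- Low flags: 0.03/4.5 = 6.7 (male); 0.04/4 = 10.0 (female).
- High over low: 14.7 (male); 10.8 (female).

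**3. High flag ÷ low flag within each row**
- Hct: 0.54/0.03 = 18.0 (male); 0.54/0.04 = 13.5 (female).
- Hb: 180/110 = 1.64; 170/100 = 1.70.
- RBC: 5.5/4.5 = 1.22; 5/4 = 1.25.

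**4. Low Hct implied by the neighbouring rows** (0.54 × low flag/high flag of that row; a consistency check, not a proposed limit)
- Male: 0.54 × 110/180 = 0.33 from Hb; 0.54 × 4.5/5.5 = 0.44 from RBC. These are 11.0 and 14.7 times the stated 0.03.
- Female: 0.54 × 100/170 = 0.32 from Hb; 0.54 × 4/5 = 0.43 from RBC. These are 7.9 and 10.8 times the stated 0.04.

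**5. What the stated limits correspond to**
- At the high-flag Hb/Hct ratio, 0.03 × 333.3 = 10.0 g/L haemoglobin (male), which is 9% of the table's own low flag of 110.
- Likewise 0.04 × 314.8 = 12.6 g/L (female), which is 13% of the low flag of 100.

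**6. Sensitivity to the benchmark.** Assume, from outside the SAP, a mean cell haemoglobin concentration of 320–360 g/L and a mean cell volume of 80–100 fL. The factor is then 10.2–11.5 (from Hb) and 12–15 (from RBC) for men, and 6.9–7.8 and 8–10 for women: about 7 to 15 overall.

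**7. Sex order.** The male limit is the higher one for Hb low (110 against 100), Hb high (180 against 170), RBC low (4.5 against 4) and RBC high (5.5 against 5). The Hct high flags are equal. Only the Hct low pair runs the other way (0.03 against 0.04).

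**The case against.** The strongest counter-argument is that little would be lost. The haemoglobin and red cell low flags still work, and at the high-flag ratios the red cell limits correspond to haematocrits of about 0.44 and 0.43. Most participants with a low haematocrit would therefore be flagged on red cell count. They would enter Listings 43–44 through that value and have all their haematology data, haematocrit included, shown in Listings 47–48. Haematocrit also appears in displays that do not use Appendix 5: the change-from-baseline Tables 2.21–2.22, the shift tables ("Summary of Hematology Laboratory Shifts From Baseline with Respect to the Normal Range - Fed" and its Fasting counterpart) and the out-of-range listings ("Listing of All Laboratory Values Outside the Normal Reference Range - Fed" and its Fasting counterpart). That all stands, and it limits the consequence.

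It is also fair that the multiplier is not exact. It assumes flags on different analytes should sit at constant red-cell indices, and the table does not follow that rule strictly: Hb/RBC is 24.4 and 25.0 pg at the low flags (110/4.5, 100/4) but 32.7 and 34.0 pg at the high flags (180/5.5, 170/5). Part of the 8-to-15 spread reflects this. It cannot explain a gap of about tenfold, and it has no bearing on the reversed sex order.

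Neither argument rescues the criterion. Tables 2.23–2.24 would still count no low haematocrit, and other flags do not correct that count.

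**Conclusion.** The two low limits are wrong as written. Against the table's own haemoglobin and red cell rows they are too low by 7.9 to 14.7 times, or about 7 to 15 times under the assumed red-cell indices, and the sex order is reversed as well. That no participant could reach such values is a physiological judgement, but the table supports it: the limits correspond to haemoglobin at 9% and 13% of its own low flags.

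The effect is confined to three places: the low haematocrit count in Tables 2.23–2.24, the haematocrit entries in Listings 43–44, and entry to Listings 47–48 on haematocrit alone. The bioequivalence analysis does not use these limits. The SAP does not show what values were intended.

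**What to change.** Before the flags are programmed, check both haematocrit low limits against the source criteria, for size and for which value belongs to which sex. Reconcile the row with its 0.54 high flag and with the haemoglobin and red cell rows. Do not simply move the decimal point: 0.3 (male) and 0.4 (female) would still have the order reversed. The correct values are for the sponsor to establish from its source.

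Section 1 states that analysis decisions are made before database freeze, so the correction belongs in the SAP rather than only in the programs. The cost is two table cells, with no new data and no new analysis.

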### **7.3. Clinical Laboratory Analyses**

Laboratory evaluations include the analyses of haematology laboratory tests, chemistry laboratory tests and urinalysis.

The haematology and chemistry data will be summarized and listed separately. Each laboratory test will be summarized at every assessed time point. Parameter values and change from baseline will be summarized separately. The shift tables with respect to normal range will be used to summarize the abnormal laboratory values. By-subject listings of all laboratory data for subjects who had any value of potential clinical importance during the study will be provided. By-subject listings of laboratory values of potential clinical importance only will also be provided.

The urinalysis analysis data will be summarized at every assessed time point.

A listing of laboratory test normal ranges will be provided. A by-subject listing of all laboratory values (including haematology, chemistry and urinalysis analysis) outside the normal reference range will be provided.

The summary will be displayed overall for Screening and by treatment group A/B for post-baseline timepoint (A: Paroxetine IR 40 mg GSKT tablet; B: Paroxetine IR 40 mg Mississauga tablet).

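### SAP 10.5.1: the red cell count limits of clinical concern are inconsistent with the haemoglobin limits beside them and would inflate the red cell flags

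*SAP*

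**What the plan says.** Section 10.5.1 belongs to "Appendix 5: Values of Potential Clinical Importance". Its haematology table gives a low and a high flag for each test under one common heading for clinical concern. Haemoglobin reads "Haemoglobin g/L Male 110 180" and, for women, "Female 100 170". The row for "Red Blood Cell Count" has limits of 4.5 and 5.5 for men and 4 and 5 for women, in units of 10^12/L. No source or rationale is given for either row.

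These limits drive planned output:

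- Table 2.23 is the "Summary of Hematology Laboratory Values Relative to Potential Clinical Importance Criteria, Day 16 or Early Withdrawal - Fed", and Table 2.24 is the same for the fasting group.
- Listing 43 is the "Listing of Hematology Abnormalities of Potential Clinical Importance - Fed", with Listing 44 for fasting.
- Listings 47 and 48 print all haematology data for participants with a flagged value. This follows section 7.3: "By-subject listings of all laboratory data for subjects who had any value of potential clinical importance during the study will be provided".

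Section 7.3 also has a separate route for values outside the normal range: "The shift tables with respect to normal range will be used to summarize the abnormal laboratory values". For haematology these are Tables 2.25 and 2.26. Listings 50 and 51 show every out-of-range value.

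**The concern.** The SAP plans two tiers of laboratory reporting: values outside the normal range, and values of potential clinical importance. The second tier is useful only if it is the more selective of the two and if related tests are judged on a similar basis. Red cell count and haemoglobin are tied together physiologically, yet the red cell band is, in relative terms, less than half as wide as the haemoglobin band. A red cell count can therefore be flagged while the haemoglobin that goes with it lies well inside its own limits.

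Safety is a secondary objective, and clinical laboratory measurements are among its endpoints (section 2.2). If the row is applied as printed, the red cell entries in the tier of potential clinical importance will be inflated. One such flag is enough to bring all of a participant's haematology data into Listing 47 or 48.

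**Working it through.** The SAP states no expected flag rate, so there is no figure of its own to reproduce. The first three steps use only the limits printed in 10.5.1. The fourth rests on assumptions.

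**1. Width of each band.** Relative half-width = (upper − lower)/(upper + lower).

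| Test | Limits | Upper/lower | Midpoint | Half-width |
|---|---|---|---|---|
| Red cells, male | 4.5–5.5 | 1.22 | 5.0 | ±10.0% |
| Red cells, female | 4–5 | 1.25 | 4.5 | ±11.1% |
| Haemoglobin, male | 110–180 | 1.64 | 145 | ±24.1% |
| Haemoglobin, female | 100–170 | 1.70 | 135 | ±25.9% |

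The red cell band is 10.0/24.1 = 0.41 (male) and 11.1/25.9 = 0.43 (female) times as wide as the haemoglobin band.

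**2. Can the two rows agree?** Haemoglobin (g/L) = red cell count (10^12/L) × haemoglobin per cell (pg). The limits coincide only where haemoglobin per cell equals the haemoglobin limit divided by the red cell limit:

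- Low limits: 110/4.5 = 24.4 pg (male); 100/4 = 25.0 pg (female).
- High limits: 180/5.5 = 32.7 pg (male); 170/5 = 34.0 pg (female).

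The low red cell limit is crossed first whenever haemoglobin per cell is above 24.4 (male) or 25.0 pg (female). The high red cell limit is crossed first whenever it is below 32.7 or 34.0 pg. Every value meets at least one of these conditions, and values in between meet both. So, holding a participant's haemoglobin per cell fixed, at least one red cell limit always fires before its haemoglobin counterpart.

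**3. The red cell limits on the haemoglobin scale.** The midpoints of the bands imply 145/5.0 = 29 pg (male) and 135/4.5 = 30 pg (female). At those values the red cell limits correspond to:

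- Male: 4.5 × 29 = 130.5 and 5.5 × 29 = 159.5 g/L.
- Female: 4 × 30 = 120 and 5 × 30 = 150 g/L.

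At 29 pg, a man with haemoglobin between 110 and 130.5, or between 159.5 and 180 g/L, has no haemoglobin flag but a flagged red cell count.

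**4. Flag rate per count, under assumption.** Assume normal values with mean m and SD s = CV × m, and the same CV for both tests (which is what a fixed haemoglobin per cell implies). Then P(flag) = Φ((lower − m)/s) + 1 − Φ((upper − m)/s). With the mean at mid-band this is 2[1 − Φ(half-width/CV)]. For men at CV 8%, 0.10/0.08 = 1.25 SD, so P = 21.1% for red cells. For haemoglobin, 35/11.6 = 3.02 SD, so P = 0.26%.

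| CV | Red cells, male | Red cells, female | Haemoglobin, male | Haemoglobin, female |
|---|---|---|---|---|
| 5% | 4.6% | 2.6% | <0.01% | <0.01% |
| 6% | 9.6% | 6.4% | <0.01% | <0.01% |
| 8% | 21.1% | 16.5% | 0.3% | 0.1% |
| 10% | 31.7% | 26.7% | 1.6% | 1.0% |

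With the mean 4% to either side of the midpoint, the red cell rate runs from 7.0% (female, CV 5%) to 37.1% (male, CV 10%). The highest haemoglobin rate is 3.0% (male, CV 10%).

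**The case against.** The strongest reply is that no stated rule is broken. The SAP does not say that limits for related tests must share a basis, the choice of limits is the sponsor's, and neither the source nor the protocol is shown. Relative width alone is weak evidence: in the same appendix sodium is 130 to 150, a ratio of 1.15, which is tighter than red cells. That is fair as far as it goes, and the ratio by itself would not carry the point. The link through haemoglobin per cell does, because it compares two tests whose values must move together.

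The size of the effect is also open. The flag rates rest on a distribution that the SAP does not give. At a CV of 5% with the mean at mid-band they are only 4.6% and 2.6% per count, and any eligibility rule on screening laboratory values in the protocol could lower them further. A reader might infer that ordinary counts would fill the haematology tables and listings; the documents do not support that at the low end of the range.

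Nor do they support two further inferences. One is that rates of potential clinical importance become meaningless for both products. A red cell limit cannot change whether a haemoglobin or platelet value is flagged; a combined count over all haematology tests would be affected only if the shells contain one, and Appendix 8 keeps the shells in separate documents. The other is that a real haematological change would be hidden. Values and change from baseline are summarised for each test at every assessed time point, and the shift tables use the normal range.

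**Conclusion.** The inconsistency stands on the printed limits alone: no haemoglobin per cell reconciles the two rows, and nothing else in the SAP explains the difference. As written, the plan would inflate the red cell entries in Tables 2.23/2.24 and Listings 43/44, and the number of participants whose full haematology data enter Listing 47 (fed) or 48 (fasting).

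The direction is firm but the amount is not. About 3% to 32% of counts would be flagged with the mean at mid-band, and up to about 37% with it 4% off-centre. The corresponding haemoglobin rate is about 0% to 3%. These figures assume normality, a CV of 5% to 10% and the same CV for both tests.

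The effect is confined to the red cell flags and what follows from them. Haemoglobin and platelet flags, change-from-baseline tables, normal-range shift tables and the bioequivalence analysis do not use these limits. It is tempting to conclude that 4.5 to 5.5 and 4 to 5 are simply the laboratory's reference limits, but the SAP does not print the reference ranges, so that remains a question for the sponsor.

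**What to change.** Before database freeze, check the red cell row of 10.5.1 against the source of the sponsor's limits, and reconcile it with the haemoglobin row so that both stand on the same clinical-concern basis. State the source in the appendix.

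If the source shows that the printed figures are only reference limits, replace them with the sponsor's clinical-concern limits for red cell count. If none exist, remove the row. Removal would leave no clinical-concern screen for red cells, but out-of-range values would still appear in Tables 2.25/2.26 and Listings 50/51.

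The cost is one row of an appendix table and the matching programming specification. No new data are needed.
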